1.1 Primary Objectives

- To evaluate the safety, tolerability, and dose-limiting toxicities (DLTs) of AGEN1884 in subjects with advanced or metastatic cancer (solid tumors or lymphoma), including but not limited to carcinoma, sarcoma, or melanoma (Phase 1); and to evaluate the safety and tolerability of AGEN1884 in subjects who have progressed during treatment with a PD-1/PD-L1 (programmed cell death protein 1/PD-1 ligand 1) inhibitor as their most recent therapy (Phase 2).
- To characterize AGEN1884 pharmacokinetics (PK).

1.2 Secondary Objectives

- To evaluate the preliminary efficacy of AGEN1884 by assessing objective response rate (ORR), disease control rate (DCR), and duration of response (DOR) per Response Evaluation Criteria in Solid Tumors (RECIST) Version 1.1.
- To evaluate the preliminary efficacy of AGEN1884 by assessing progression-free survival (PFS) and overall survival (OS).

1.3 Exploratory Objectives

- To explore biomarkers that may predict pharmacologic activity or response to AGEN1884.
- To characterize the effect of AGEN1884 on tumor tissue obtained post-treatment, if available.

2. Background

2.1 Investigational Agent: AGEN1884

AGEN1884 is a novel, fully human monoclonal immunoglobulin G1 (IgG1) antibody designed to block cytotoxic T lymphocyte—associated protein 4 (CTLA-4), a key negative regulator of T-cell responses. Blocking CTLA-4 with an antibody enhances antitumor immune responsiveness by inhibiting the downregulation of T-cell activation. In this first-in-human trial, AGEN1884 will be evaluated as monotherapy in subjects with advanced and/or refractory malignancies, including those who have progressed during treatment with a PD-1/PD-L1 inhibitor as their most recent therapy.

2.1.1 Supporting Nonclinical Data

AGEN1884 selectively binds with high affinity to human CTLA-4 and cross-reacts with cynomolgus monkey (*Macaca fascicularis*) CTLA-4. However, AGEN1884 does not cross-react with rodent CTLA-4 or CTLA-4-related members of the CD28 superfamily. AGEN1884 potently blocks the interaction of CTLA-4 with CD80 and CD86, resulting in increased levels of interleukin 2 from T-cell receptor (TCR)—activated T cells cultured from peripheral blood mononuclear cells (PBMCs). By contrast, when soluble AGEN1884 is added to human PBMCs or whole blood in the absence of TCR activation, cytokines are not induced. Cytokine production in the absence of TCR stimulation would be predictive of cytokine release syndrome *in vivo*. Importantly, activated T cells cultured in the presence of AGEN1884 showed no evidence of reduced cytokine production, thereby excluding any agonistic inhibitory signals delivered by this

Confidential Page 19 of 78

antibody. Consistent with its ability to engage cynomolgus monkey CTLA-4, AGEN1884 enhanced T cell-dependent antibody responses in animals immunized with a hepatitis B vaccine.

CTLA-4 is also expressed by regulatory T cells (Tregs), which can impair tumor immunity by multiple suppressive mechanisms (Wing et al., 2008; Zou, 2006). One such mechanism involves Treg-expressed CTLA-4 mediating the physical removal of CD80 and CD86 from the surface of activated antigen-presenting cells (APCs) by a process termed trans-endocytosis, which can attenuate the immune-stimulatory potential of APCs (Qureshi et al.). Emerging clinical and preclinical study data support a secondary mechanism of action for anti-CTLA-4 antagonist antibodies involving the deletion of Tregs (Bulliard et al., 2013; Marabelle et al., 2013; Romano et al., 2015; Selby et al., 2013; Simpson et al., 2013). This mechanism involves the co-binding of anti-CTLA-4 antibodies to Tregs located within the tumor and fragment-crystallizable gamma receptor (FcyR)-expressing effector cells (e.g., natural killer or myeloid cells), resulting in antibody-dependent cellular cytotoxicity (ADCC) or antibody-dependent cellular phagocytosis. The elimination of tumor-associated Tregs, which contribute to tumor immunity by dampening the activation of effector T cell to tumor-associated antigens, is considered to be a major obstacle in achieving effective antitumor immunity during immunotherapy (Zou, 2006). Consistent with an IgG1k fragment crystallizable (Fc) region, AGEN1884 can bind to FcyRs expressed by effector immune cell populations and mediate ADCC activity against target cells expressing high levels of CTLA-4. Also consistent with its IgG1 k Fc region, AGEN1884 showed in vitro evidence of complement-dependent cytotoxicity toward CTLA-4-expressing target cells.

AGEN1884 PK studies have been conducted in cynomolgus monkeys following both single and repeated intravenous (IV) administration. AGEN1884 has a biphasic disposition with a terminal elimination half-life ($t_{1/2}$) of between 8 and 20 days. Exposure (maximum drug concentration at steady-state [C_{max-ss}] and area under the drug concentration-time curve [AUC]) increased in an approximately dosage-proportional manner. No gender difference was noted for plasma drug exposure (C_{max-ss} or AUC). Accumulation was observed, as exposure was approximately twice as high after multiple weekly administrations.

Repeated-administration IV toxicology studies have been conducted in cynomolgus monkeys, including a 1-month Good Laboratory Practice (GLP) study. In both studies, AGEN1884 was administered by a slow IV bolus once weekly (days 1, 8, 15, 22, and 29) at dosages of 0 (vehicle), 5, 30, and 100 mg/kg AGEN1884. No evidence of any toxicity was observed after a thorough examination of in-life, clinical pathology (including cytokines), flow cytometry, and macroscopic and histopathological examinations. A GLP tissue cross-reactivity study with human tissues indicated binding to plasma membranes of mononuclear cells in a number of tissues.

The maximum recommended starting dose (MRSD) was based on the MRSD derived from the minimally anticipated biological effect level (MABEL). The proposed starting dose for this study is 0.1 mg/kg of AGEN1884, which is based on *in vitro* pharmacology and *in vivo* PK and toxicology studies. This dosage is higher than the calculated MABEL of 0.042 mg/kg, but is believed to represent a safe starting dosage that will provide improved opportunity for pharmacological activity in Phase 1 subjects. Please refer to the Investigator's Brochure for further details.

Confidential Page 20 of 78

2.2 Rationale

CTLA-4 is one of various down regulators of the immune response, known as an inhibitory checkpoint, and blocking it with an anti–CTLA-4 antibody has been demonstrated to enhance immune responsiveness by inhibiting downregulation of T-cell activation. An IgG1 anti–CTLA-4 antibody has demonstrated robust clinical efficacy, and has received approval in the United States for the treatment of metastatic melanoma, and in Europe for previously treated metastatic melanoma (Page et al.m 2013).

The clinical efficacy associated with blockade of CTLA-4 has also been associated with toxicity as the result of immune activation. Moreover, only a select group of patients, even among melanoma patients, will respond to CTLA-4 blockade alone (Page et al., 2013). The combination of CTLA-4 blockade with PD-1 blockade was recently shown to be more effective than targeting either pathway alone, but still had substantial side effects suggestive primarily of toxicity from CTLA-4 blockade (Larkin et al., 2015). Combining a CTLA-4 inhibitor such as AGEN1884 with PD-1 blockade or other immunotherapies therefore remains an attractive goal in immuno-oncology. Alternate combination approaches to the development of AGEN1884 may ameliorate the side effects of CTLA-4 blockade while focusing immune stimulation to the benefit of patients with tumor types for which immunotherapy does not currently work, and patients with melanoma who cannot tolerate CTLA-4 blockade with the approved antibody as currently administered.

The present study will seek to define the safety and maximum tolerated dose (MTD) of single-agent AGEN1884, and include expansion of enrollment at the MTD or maximum planned dose level to further explore the activity of AGEN1884 monotherapy in subjects with advanced or refractory cancer, including those who have progressed during treatment with an approved or investigational PD-1/PD-L1 inhibitor as their most recent therapy (2-6 weeks prior to first dose of study drug). The Phase 2 portion of the study will also include expansion of enrollment at 1 mg/kg and 3 mg/kg to further explore the activity of AGEN1884 as a monotherapy. In the expansion phase, subjects who have received previous treatment with immunotherapeutic agents (except those who received previous treatment with anti–CTLA-4 agents) will be allowed to enroll in order to better understand the safety of sequential treatment with AGEN1884 in what is becoming a common clinical practice due to the approval of multiple PD-1– and PD-L1– targeting agents.

Moreover, substantial clinical activity has been observed when PD-1/PD-L1 inhibition and CTLA-4 inhibition are combined sequentially (Weber et al., 2016). Although the half-life of nivolumab is 17-25 days (Bristol-Meyers Squibb, 2013), its occupancy of PD-1 on circulating T cells has a mean plateau of 72% for at least 59 days, with PD-1 blockade persisting even with undetectable serum nivolumab concentrations (Brahmer et al., 2010); therefore, substantial inhibition of PD-1 would be expected to continue in the PD-1/PD-L1 cohorts at the time of AGEN1884 treatment initiation. The results of this single-agent study will inform the further development of AGEN1884.

3. Investigational Plan

3.1 Overall Study Design

This is an open-label, Phase 1/2, multicenter study to evaluate the safety, PK, and pharmacodynamics, and activity of an anti–CTLA-4 human monoclonal antibody (AGEN1884)

Confidential Page 21 of 78

[figure not shown]
in subjects with advanced or refractory cancer. The Phase 1 portion of the study has been completed and contained a 3+3 dose escalation phase evaluating AGEN1884 at 0.1, 0.3, 1, 3, and 6 mg/kg dose levels, and an expansion phase at 1 mg/kg and 3 mg/kg. Dose levels >6mg/kg were not planned.

The Phase 2 portion of the study includes subjects who have progressed during treatment with an approved or investigational PD-1/PD-L1 inhibitor as their most recent therapy (2-6 weeks prior to first dose of study drug). The dose for the Phase 2 portion of the study was based on clinical data from the Phase 1 portion evaluating AGEN1884 as monotherapy. At the time of this amendment, based on data from the Phase 1 dose escalation, 1 mg/kg was chosen as the starting dose for Phase 2.

The study design is depicted in Figure 1.

Confidential Page 22 of 78

Figure 1: Study Design

^{*} Additional subjects may be enrolled in Phase 2 to either the HCC or non-HCC populations as necessary to ensure that 20 subjects are evaluable for additional PK assessments (i.e., 3 additional timepoints, see Section 5.3).

AGEN1884 will be administered on Day 1 of each 3-week cycle for 4 cycles. At a 12-week evaluation timepoint (based on 2 scans of tumor assessment), subjects may continue to receive AGEN1884 every 3, 6, or 12 weeks (± 7-days), for a maximum duration of 1 year of treatment, provided they were not diagnosed with disease progression and were tolerating the study drug. The appropriate schedule will be based on discussion with the medical monitor. Subjects who progressed during the treatment period, yet still have clinical benefit from treatment, may continue treatment post-progression with the medical monitor's approval. The dosing schedule for these subjects should be determined based on discussion with the medical monitor.

Phase 1

The Phase 1 portion of the study was to enroll overall approximately 40 adult subjects with refractory, advanced cancer (solid tumors or lymphoma), including those who have progressed during treatment with an approved or investigational PD-1/PD-L1 inhibitor as their most recent therapy (2-6 weeks prior to first dose of study drug). The 3+3 dose escalation started at 0.1 mg/kg, as shown in Table 1. (Dose levels beyond 6 mg/kg are not currently planned.) The bio-pharmacological properties of the antibody suggested that this dose escalation plan would include evaluation of doses within a safe and clinically active range. Dose escalation continued until the MTD was reached or the maximum planned dose level (6 mg/kg) was shown to be safe after cohort expansion occurred at the 1 mg/kg and 3 mg/kg dose levels. The MTD is defined as the dose below which 2 DLTs are observed (see Section 3.1.2.2 for definition of DLTs).

The cohorts and dose levels are shown in Table 1. Information about stopping rules for toxicity is provided in Section 3.1.2.3.

Table 1: AGEN1884 Dose Levels and Cohorts

Dose Level Cohort	AGEN1884 Dose (mg/kg)	Study Phase	Number of Subjects
Phase 1			
1 (starting dose)	0.1	Dose escalation	3-6
2	0.3	Dose escalation	3-6
3	1	Dose escalation and expansion (a)	10
4	3	Dose escalation and expansion (a)	10
5	6	Dose escalation	3-6
Phase 2			
	1	Subjects who progressed on a PD-1/PD-L1 inhibitor as last prior therapy (b)	Up to 60 (c)

DLT: dose-limiting toxicity; HCC: hepatocellular carcinoma; PD-1: programmed cell death protein 1; PD-L1: ligand 1 of programmed cell death protein 1.

^a Includes 3-6 subjects for DLT evaluation plus additional subjects to achieve up to 10 evaluable subjects in the cohort.

^b Includes subjects who progressed during treatment with an approved or investigational PD-1/PD-L1 inhibitor as their most recent therapy (2-6 weeks prior to first dose of study drug). Includes subjects in Phase 2 with HCC who progressed during treatment with an approved or investigational PD-1/PD-L1 inhibitor as their most recent therapy (2-6 weeks prior to first dose of study drug). Of the 40 subjects in this cohort at the 1.0 mg/kg dose level: 1) Approximately 20 subjects diagnosed with HCC will be enrolled; 2) The enrollment of non-HCC will be approximately 40 subjects.

^c Additional subjects may be enrolled to either the HCC or non-HCC populations as necessary to ensure that 20 subjects are evaluable for additional PK evaluation (i.e., 3 additional timepoints, see Section 5.3).

The DLT observation period was defined as 28 days from initial administration of AGEN1884. Based on experience with other anti–CTLA-4 antibodies, this allowed for infusion-related toxicities and other early onset immune-related toxicities, such as skin-related adverse events, to be observed during the DLT observation period without unnecessarily prolonging the observation period. Additionally, some immune-related toxicities from CTLA-4 inhibition were likely to occur later in therapy than 42 days (Weber et al., 2013), the last day before dose number 3 would be due for subjects on this study. Therefore, late toxicities were evaluated by the Safety Review Committee (SRC) per Section 3.1.1 to ensure that related toxicities are still considered in DLT review even if they fall outside of the observation period.

Once the 1 mg/kg and 3 mg/kg dosages were declared safe, these cohorts were expanded to include overall 10 evaluable subjects in each cohort before enrolling subjects into the 6 mg/kg dose cohort. Dose escalation continued until the MTD was reached, or the maximum planned dose level (6 mg/kg) was shown to be safe after cohort expansion occurred at the 1 mg/kg and 3 mg/kg dose levels. The expansion cohorts allowed collection of additional PK/anti-drug antibody (ADA) and safety data, which will be used to plan development of combination (AGEN1884 plus drug[s]) strategies. As several anti–PD-1 and anti–PD-L1 products are already commercially available, many subjects receive these therapies as standard of care, therefore subjects who previously received these therapies were allowed to enroll in these expansion cohorts to help to better understand the safety of sequential treatment with AGEN1884.

Disease response assessments by RECIST was to be performed at Study Week 6, Week 12 and Q6w for subjects assigned to 3- or 6-w treatment schedule, or Q12w for subjects assigned to 12-w treatment schedule until off-disease response evaluation criteria are met.

Phase 2

Up to 60 subjects will be enrolled at the recommended Phase 2 dose of 1.0 mg/kg. Phase 2 consists of subjects who have progressed during treatment with an approved or investigational PD-1/PD-L1 inhibitor as their most recent therapy (2-6 weeks prior to first dose of study drug). For this phase:

- Approximately 20 subjects with advanced HCC will be enrolled.
- The enrollment of non-HCC will be approximately 40 subjects.

Note: additional subjects may be enrolled to either the HCC or non-HCC populations as necessary to ensure that 20 subjects are evaluable for the purpose of the additional PK evaluation (i.e. 3 additional timepoints, see Section 5.3).

Disease response assessments by RECIST to be performed at Study Week 6, Week 12 and Q6w for subjects assigned to 3- or 6-w treatment schedule, or Q12w for subjects assigned to 12-w treatment schedule until off-disease response evaluation criteria are met.

Subjects in both phases were evaluated for PK, PD, disease response, and safety, as determined through physical examination, vital signs, 12-lead electrocardiograms (ECGs), clinical laboratory tests, cytokine and lymphocyte subset measurements, and adverse events (Table 10).

3.1.1 Safety Review Committee

Study safety review will be presided over by the SRC, composed of the clinical investigators and medical monitor/study sponsor. The SRC will be convened regularly, including at the end of a cohort, once the protocol-defined criteria for dose escalation are met, to review all available

Confidential Page 25 of 78

subject safety data in advance of providing formal notification to investigators that they may proceed to enroll subjects in the escalated dose cohort. The SRC will also be convened to evaluate all subjects on study when ≥2 adverse events are noted that are possible DLTs on a dose level and/or discuss additional toxicities that may warrant dose de-escalation, as described in Section 3.1.2.3. In Phase 2, the SRC will continue to meet at a frequency specified in the Safety Review Charter.

3.1.2 Dose-Limiting Toxicity Evaluation

3.1.2.1 Dose Escalation Procedures in Phase 1

The initial starting dose was 0.1 mg/kg and the first subject was enrolled to confirm safety at this level, which is near the MABEL dose. A minimum of 3 subjects were to be enrolled in each cohort. The first 2 subjects in each dosing cohort were to be enrolled ≥24 hours apart, and enrollment of the second subject did not proceed unless the first subject tolerated the therapy without DLT within the first 24 hours following the start of the infusion of the first subject. Each subject was observed for a DLT observation period of 28 days from initiation of AGEN1884 treatment, and 3 subjects must have been able to receive and tolerate the first 2 doses of AGEN1884 without DLTs during this observation period before the next cohort began enrollment. The dose was to be escalated if 0 of the first 3 evaluable subjects enrolled had a DLT. If 1 of the first 3 evaluable subjects enrolled had a DLT, then the cohort was to be expanded to include 3 additional evaluable subjects; if no DLT occurred in the additional 3 subjects, then the dose was to be escalated. If a DLT occurred in >2 subjects in the total cohort, the MTD was deemed to be exceeded, and the prior dose level was evaluated to determine the MTD by increasing enrollment to 6 subjects. If the prior dose level was already deemed to be safe and enrolled 6 subjects, then it was defined as the MTD. Alternate dosing schedules of AGEN1884 could have been explored depending on PK, pharmacodynamics, and safety results.

If 0.1 mg/kg exceeded the MTD (i.e., does not pass DLT evaluation), the sponsor and investigators considered alternate dose schedules (e.g., every 4 weeks) based on available safety, PK, and pharmacodynamics data. If an alternate schedule was tested and determined to be safe, re-escalation of AGEN1884 proceeded according to Table 1.

Additional subjects were enrolled in a cohort to achieve the minimum of 3 evaluable subjects at each dose level. Subjects who dropped out or who had dose interruptions/reductions that resulted in a subject being non-evaluable for DLTs were considered non-evaluable. Dose modifications in the DLT period due to any related toxicity were considered a DLT. Subjects who experienced a DLT during the dose-escalation portion of the study were discontinued from study drug. Intrasubject dose escalation was not permitted.

When accrual for the 3 mg/kg dose cohort was paused for safety assessment and DLT observation, expansion of the 1 mg/kg cohort began to enroll a total of 10 evaluable subjects.

Once 3 mg/kg was determined to be safe by the SRC, the 3 mg/kg dose cohort was expanded to enroll a total of 10 evaluable subjects; backfilling into the 1 mg/kg dose cohort was paused during this time. If the 1 mg/kg dose cohort did not reach 10 subjects, additional subjects were enrolled in the 1 mg/kg cohort after 10 evaluable subjects were enrolled in the 3 mg/kg cohort. Once 1 mg/kg and 3 mg/kg cohorts completed expansion and had each enrolled 10 evaluable subjects, dose escalation resumed at 6 mg/kg, according to the protocol. If any of the first 3

Confidential Page 26 of 78

evaluable subjects enrolled at the maximum planned dose of 6 mg/kg experienced DLT, an additional 3 subjects were enrolled for a total of 6 subjects at the maximum planned dose.

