	Subjects will be excluded if they have had a previous severe hypersensitivity reaction to another fully human monoclonal antibody, history of primary of secondary immunodeficiency or autoimmunity, or received anticancer medications or other investigational drugs within protocol-defined intervals before the first administration of study drug.		
Number of Subjects, Accrual, and Study Duration	Overall, approximately 100 subjects will be enrolled in Phase 1 and Phase 2. In Phase 2, up to 60 of these subjects must have experienced progression with a PD-1/PD-L1 inhibitor as their most recent therapy (2-6 weeks prior to first dose of study drug). Approximately 20 subjects in Phase 2 will have advanced HCC.		

Confidential Page 6 of 78

	Study duration will be approximately 5 years (including enrollment and follow-up).			
Study Design and Dosing	This is an open-label, Phase 1/2, multicenter study to evaluate the safety, PK, pharmacodynamics, and activity of an anti–CTLA-4 human monoclonal antibody (AGEN1884).			
	The Phase 1 portion of the study is completed. It enrolled adult subjects with refractory, advanced cancer. The 3+3 dose escalation evaluated AGEN1884 at 0.1, 0.3, 1, 3, and 6 mg/kg dose levels. It also included an expansion phase at 1 mg/kg and 3 mg/kg. Dose levels >6 mg/kg were not planned. The biopharmacological properties of the antibody indicated that this dose escalation plan would include evaluation of doses within a safe and clinically active range. Dose escalation continued until the MTD was reached or the maximum planned dose level (6 mg/kg) was shown to be safe (i.e., passes DLT evaluation). The MTD was defined as the dose below which 2 DLTs are observed among 3 subjects treated at a given dose level.			
	Based on data from the Phase 1 dose escalation, 1 mg/kg was chosen as the starting dose in Phase 2. Phase 2 consists of approximately 40 subjects who have progressed during treatment with an approved or investigational PD-1/PD-L1 inhibitor as their most recent therapy (2-6 weeks prior to first dose of study drug). For this phase:			
	Approximately 20 subjects with advanced HCC will be enrolled.			
	• The enrollment of non-HCC will be approximately 40 subjects.			
	Note: additional subjects may be enrolled to either the HCC or non-HCC populations as necessary to ensure that 20 subjects are evaluable for the additional PK evaluation (i.e., 3 additional timepoints, see Section 5.3).			

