3.1.2.2 Definition of Dose-Limiting Toxicity

With exceptions discussed below, a DLT is defined as a grade ≥3 adverse drug reaction (ADR), according to the National Cancer Institute (NCI) Common Terminology Criteria for Adverse Events (CTCAE) Version 5, occurring in the DLT evaluation period (i.e., 28 days after the initial administration of AGEN1884) in subjects enrolled in the phase 1 dose escalation.

The SRC recognizes that in the absence of prior human experience with AGEN1884, a conservative approach should be adopted in ascribing the relevance of the treatment-related toxicity to drug. Treatment-emergent serious adverse events (SAEs) will be ascribed as related to drug except in cases in which a clear relationship to the underlying disease or recognized comorbidities are evident. For this trial, the MTD is defined as the highest dose at which <2 of 6 subjects experience a DLT.

A DLT is specifically defined as any one of the following:

- Grade ≥ 2 uveitis, eye pain, or blurred vision that does not respond to topical therapy.
- Any grade ≥3 toxicity that is possibly, probably, or definitely related to AGEN1884
 occurring during the DLT evaluation period (28 days after initial administration of
 AGEN1884), except for any of the following:
 - Grade 3 infusion-related reaction resolving within 6 hours of dosing and controlled with medical management.
 - Transient (≤6 hours) grade 3 flu-like symptoms or fever, which are controlled with medical management.
 - Transient (≤24 hours) grade 3 fatigue, local reactions, headache, nausea, or emesis that resolves to grade ≤1.
 - Grade 3 diarrhea, skin toxicity, or liver function test (LFT), (alanine aminotransferase [ALT], aspartate aminotransferase [AST], or gamma glutamyltransferase [GGT]) increase that resolves to grade ≤1 within 7 days after medical management (e.g., immunosuppressant treatment) has been initiated.
 - Single laboratory values out of normal range that are unlikely related to trial treatment according to the investigator, do not have any clinical correlate, and resolve to grade ≤1 within 7 days with adequate medical management.
 - Tumor flare phenomenon, defined as local pain, irritation, or rash localized at sites of known or suspected tumor.

Subjects who do not complete the DLT observation period and do not receive 2 doses of AGEN1884 during the DLT observation period for reasons other than a DLT will be replaced.

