3.1.2.3 Stopping Rules in Phase 1 for Enrollment Based on Toxicities

• If 2 or more DLTs occur at Dose Level 1 (0.1 mg/kg), then study enrollment will stop and evaluation of biologic and clinical activity will be completed for Dose Level 1. If there is a rationale to proceed at or near Dose Level 1 based on clinical or biological activity from

Confidential Page 27 of 78

enrolled subjects, then Agenus will redesign the study with new dose levels and potentially a new dose frequency, both of which would be intended to decrease the dose intensity on study, and approach the Food and Drug Administration (FDA) for guidance before activating such a redesigned study.

• The SRC will meet to review the dose cohort under evaluation as well as safety of the full cohort under evaluation. Should ≥2 subjects on any dose level experience toxicities that meet DLT criteria but occur after the DLT evaluation period, enrollment will be held and the occurrences would be thoroughly evaluated by the SRC. Should these events be consistent with DLTs, for instance, from immune-related toxicities, they will be evaluated for relatedness to AGEN1884. The SRC will evaluate the events and de-escalate the dose level due to immune-related adverse events meeting DLT criteria that occur beyond the DLT evaluation period.

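### Protocol 3.1.2.1 as supplied calls the MTD exceeded only at more than 2 DLTs, while 3.1.2.2 requires fewer than 2 of 6; a level ending at exactly 2 of 6 cannot be the MTD but is not labelled exceeded and triggers no step back

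*Protocol*

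**What the plan says.** The Phase 1 rules appear in several places of the protocol.

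- **3.1.2.1, escalation:** escalate after 0 of 3, or after 1 of 3 followed by 0 of 3 more. The general rule names expansion only after 1 of 3. Then: "If a DLT occurred in >2 subjects in the total cohort, the MTD was deemed to be exceeded". Being exceeded is what triggers the return to the prior dose level.
- **3.1.2.2, definition:** "the MTD is defined as the highest dose at which <2 of 6 subjects experience a DLT". This is the only definition that is explicit about six subjects.
- **3.1, Phase 1:** "The MTD is defined as the dose below which 2 DLTs are observed", with no denominator.
- **Synopsis, Study Design and Dosing:** "The MTD was defined as the dose below which 2 DLTs are observed among 3 subjects treated at a given dose level".
- **3.1.2.3, stopping rules:** "If 2 or more DLTs occur at Dose Level 1 (0.1 mg/kg), then study enrollment will stop". For late events: "Should ≥2 subjects on any dose level experience toxicities that meet DLT criteria but occur after the DLT evaluation period, enrollment will be held".
- **3.1.1:** the Safety Review Committee is convened "when ≥2 adverse events are noted that are possible DLTs on a dose level".
- **3.1.2.1, last paragraph:** at 6 mg/kg, a DLT in any of the first 3 evaluable subjects leads to 3 more, for a total of 6. No upper limit is set on the number of DLTs among those first 3.

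Section 2.2 gives defining the MTD as an aim of the study, and 1.1 lists Phase 1 DLTs within the primary objective. SAP 5.3 plans a separate final analysis for each phase. The supplied SAP covers Phase 2 only (SAP 2).

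**The concern.** Exactly 2 of 6 falls between the two thresholds. More than 2 means 3 or more, so 3.1.2.1 does not call the level exceeded. Fewer than 2 of 6 means 0 or 1, so 3.1.2.2 does not allow it to be the MTD. The step back in 3.1.2.1 depends on the label, so as supplied it is not triggered.

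The gap matters most at 6 mg/kg, the top planned dose, because no higher level exists at which the question would settle itself. What is at stake is how the Phase 1 report states the MTD. Protocol 6.3 defines a DLT-evaluable set, but 6.4.1 lists no DLT or MTD summary, and no Phase 1 analysis plan is among the documents. Nothing supplied settles which threshold that report will use.

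The 6 mg/kg expansion sentence is a separate matter. Once 2 or 3 of the first 3 have a DLT, fewer than 2 of 6 can no longer be reached, yet the sentence would still add 3 subjects.

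**Working it through.** **Classifying the outcomes at 6 mg/kg, as supplied**

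| Outcome | 3.1.2.1 (>2) | 3.1.2.2 (<2 of 6) |
|---|---|---|
| 0 of 3, or 1 of 6 | meets the rule used for escalation | compatible with MTD |
| 2 of 6 | no escalation, not exceeded, no step back | not the MTD |
| 3 or more of 6 | exceeded, step back | not the MTD |

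The middle row is the gap. It also exists at 0.3, 1 and 3 mg/kg. At 0.1 mg/kg, 3.1.2.3 covers 2 or more DLTs. With ≥2 in 3.1.2.1 the middle row becomes exceeded and the gap closes.

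**Size**

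The plan states no operating characteristics, so there is no figure of its own to reproduce. The true DLT rate p is not given either; I assume 10%, 20%, 30% and 40%, independent between subjects. Write q = 1 − p.

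- Exactly 2 of 6 at 6 mg/kg, with expansion after any DLT in the first 3, arises as 1 of 3 then 1 of 3, or 2 of 3 then 0 of 3: (3pq²)² + (3p²q)q³ = 12p²q⁴. The maximum is at p = 1/3: 12 × (1/9) × (16/81) = 26.3%.
- If only 1 of 3 leads to expansion, as in the general rule, the second path drops out: 9p²q⁴, at most 19.8%. This form also applies to the middle dose levels.
- At least 2 of the first 3: 3p²q + p³. All 3 of the first 3: p³.
- Exceeded at 6 mg/kg under ≥2: 1 − q³ − 3pq⁵. Under >2, subtract 12p²q⁴.

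| Assumed p | 10% | 20% | 30% | 40% |
|---|---|---|---|---|
| Exactly 2 of 6 at 6 mg/kg, as written | 7.9% | 19.7% | 25.9% | 24.9% |
| Exactly 2 of 6, expansion only after 1 of 3 | 5.9% | 14.7% | 19.4% | 18.7% |
| At least 2 of the first 3 | 2.8% | 10.4% | 21.6% | 35.2% |
| All 3 of the first 3 | 0.1% | 0.8% | 2.7% | 6.4% |
| Exceeded at 6 mg/kg under >2 | 1.5% | 9.5% | 24.6% | 44.2% |
| Exceeded at 6 mg/kg under ≥2 | 9.4% | 29.1% | 50.6% | 69.1% |

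**What the expansion sentence contradicts**

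Under a literal >2, 3.1.2.1 names no action for 2 of 3, so the 6 mg/kg sentence fills a gap there and only 3 of 3 contradicts that section (the p³ row). Under ≥2, both 2 of 3 and 3 of 3 would already have exceeded the MTD (the row above it). With either symbol, at least 2 of the first 3 puts the 3.1.2.2 criterion out of reach.

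**The case against.** **The symbol.** The main point rests on one character in machine-read text. Bars differ elsewhere: the NYHA criterion reads <II in the synopsis and ≤II in 3.2.1, and one HCC dose-delay rule reads ≥3 times baseline in 4.1.2 and >3 times in Table 6. Other numeric triggers for DLTs act at 2, so ≥2 is the likelier intention. This stands as a reason to check before changing anything. It is not proof, because a ≥ survives in the same paragraph of 3.1.2.1 (the 24-hour spacing of the first two subjects).

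**No status at all?** A reader might infer that 2 of 6 is wholly undefined, or could be named the MTD. The documents do not support that. Section 3.1.2.2 rules it out as the MTD, 3.1.2.1 never escalates after it, and 3.1.1 convenes the committee. Only the label and the step back are open. Even that is narrow at 6 mg/kg: by then 3 mg/kg was to have been found safe with 10 evaluable subjects, so a step back would have made it the MTD directly under 3.1.2.1.

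**Shown to be safe?** A reader might join the synopsis wording, "the maximum planned dose level (6 mg/kg) was shown to be safe (i.e., passes DLT evaluation", to the remark in 3.1.2.1 that equates exceeding the MTD with failing DLT evaluation, and conclude that 2 of 6 passes. That remark concerns 0.1 mg/kg, where 3.1.2.3 stops enrollment at 2 or more DLTs. No section says that not exceeded means passed.

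**Late versus early DLTs?** The enrollment hold for 2 late DLTs is a pause for review, whereas 3.1.2.1 gives an MTD verdict. Two early DLTs also bring in the committee, so this is not a further contradiction.

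**Consequence.** Phase 1 is finished, and the MTD is neither a listed objective nor an endpoint; it is an aim in the rationale. This stands and limits the point to reporting.

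**Conclusion.** The concern holds in a limited form and is a minor correction. As supplied, 3.1.2.1 and 3.1.2.2 use different thresholds, and a level above 0.1 mg/kg that ends at exactly 2 of 6 is left without the exceeded label and without the step back. If the original reads ≥2, that part disappears. The synopsis denominator of 3 and the open-ended 6 mg/kg expansion are inconsistent with the six-subject criterion under either symbol.

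The probability of 8% to 26% for 2 of 6 at 6 mg/kg depends on assumed DLT rates of 10% to 40% and on the expansion sentence as written. It shows that the outcome is not remote, not that it happened. A reader might take the expansion sentence as evidence that 6 mg/kg was in fact expanded, but it is conditional, and no document reports a DLT count or an expansion there. The effect on the MTD statement may be nil. No subject's dosing is affected, because Phase 2 uses 1 mg/kg.

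**What to change.** 1. Check the symbol in the original protocol.
2. Use one criterion in the synopsis, 3.1 and 3.1.2.1: the MTD is the highest dose with DLTs in fewer than 2 of 6, and a level is exceeded at 2 or more. Because 3.1.2.1 describes completed conduct, state the rule actually applied if it differed rather than overwrite it.
3. In the Phase 1 report, give DLTs over evaluable subjects for each level, the rule that the Safety Review Committee used, and whether 6 mg/kg was expanded and after how many DLTs in the first 3.
4. Do not report 6 mg/kg as the MTD, or as having passed DLT evaluation, if it had 2 or more DLTs.

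The cost is a few words in three places and one table from existing data. No dosing changes. The downside is that the reported MTD may be lower.
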